9.2 SAMPLE SIZE DETERMINATION

Sample Size and Power. Our target sample size for the first trial is 14,442 patients, 4814 patients in each of the three study arms. The calculations below employ 80% power, overall Type I error rate of .05 with a Bonferroni correction for 3 pairwise comparisons of study arms (.05/3=.0167), and 2-sided hypothesis testing. Based on our prior analyses,^{26,27} we anticipate death or health plan disenrollment in 9.9% of sampled patients within 3 months of the intervention (receipt of the letter), with the remaining 90.1% contributing data in the 6-month interval of interest (days 91-270 post-intervention) – that is, we anticipate a per-arm sample size of $4814 \times .901 = 4337$.

For analyses of the primary outcome, absence of dispensing of targeted inappropriate prescription classes in days 91-270, we anticipate censoring in this interval for 13.5% of participants based on prior data. To make maximal use of observed data, we will use survival analysis to model time until an inappropriate prescription (a “failure”) in days 91-270. Detectable pairwise between-arm differences (e.g., between usual care and an intervention arm) are presented in Table 2 below for a range of possible percentages for “failure” = inappropriate prescribing of the targeted drug.

Table 2. Detectable pairwise between-arm differences in hazard of inappropriate prescription classes in days 91-270

Percent with inappropriate prescribing of targeted drug (“failure”), Study Arm 1	Detectable hazard ratio for inappropriate prescribing, Arm 2 versus Arm 1
40	.8860
50	.8979
60	.9067
70	.9136
75	.9165
80	.9192
85	.9216
90	.9239
95	.9260
99	.9267

For the range of “failure” percentages examined here, which reflect those seen in Martin et al,³ detectable hazard ratios range from 0.89 to 0.93. For example, if 75% of participants randomized to Arm 1 are observed to have a “failure” (prescription for a targeted inappropriate medication) by day 270, the detectable hazard ratio for an inappropriate prescription for Arm 2 versus Arm 1 is 0.9165, a

8.35% reduction in risk; the corresponding detectable “failure” probability for Arm 2 = 0.7193, a difference smaller – i.e., more precise – than that seen in Martin et al.³ Calculations for the secondary outcome of ≥50% reduction in dose are parallel.

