For additional secondary outcomes, such as per-patient number of hospitalizations or ED visits, based upon prior data (mean of 0.35 hospitalizations per 6-month period and 0.4 ED visits per 6-month period), we will be able to detect rate ratios of 0.8856 and 0.8927, respectively (corresponding to intervention-related reductions of 11.4% and 10.7%), accounting for censoring due to death or disenrollment. For between-arm differences in mortality, assuming usual care 6-month mortality of 6.3% – likely an underestimate given a lag in ascertainment – and 7.6% censoring due to disenrollment based on information provided by the participating health plans, the detectable hazard ratio is 0.7356 corresponding to per-arm survival percentages of 93.7% versus 95.33% (absolute difference of 1.63%).

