9.4.3 ANALYSIS OF THE SECONDARY ENDPOINT(S)

Secondary outcomes. These will also be assessed specific to the 6-month observation period (days 91-270 following mailing/intervention) based on health plan claims data including:

- a) Any dose reduction of each of the targeted medications, assessed at the participant level using health claims data (outpatient dispensings).
- b) Percentage of patients with prevalence of polypharmacy (defined as >5 active prescriptions for different oral agents)³²
- c) Rates of emergency room visits; rates of hospitalizations; rates of non-acute institutional stays (e.g., skilled nursing facilities); overall health care utilization (number of outpatient visits, days hospitalized, emergency department visits, and non-acute institutional days).
- d) In-hospital all-cause mortality
- e) Switching within classes

We will use administrative claims data to identify encounters of interest (ED visits, hospitalizations, non-acute institutional stays, outpatient visits) and only assess oral formulations for medications.

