Measurement of Dose Reduction. We will consider dose reduction for each selected drug as being a $\geq 50\%$ decrease in the mean daily dose comparing the 6 months immediately prior to the randomization with the 6-month study window period. (day 91-day 270). We will measure average daily dose using dates of prescription dispensing, duration of prescription dispensing and strength of the prescription. We will measure the dose reduction as a dichotomous variable defined as the proportion of patients who achieved a more than 50% dose reduction in the daily dose during the study window period (day 91 to day 270) compared to the 6-month period prior to randomization. Measurement of dose reduction over 6 month follow-up requires participants to complete follow-up through end of observation period (day 270). Censored participants – that is, those who have less than 6 months in days 91-270 – will be excluded for the analysis of dose reduction. Analyses will adjust for correlates of missing data. Analyses for post-intervention polypharmacy prevalence will be analogous. We will identify participants with evidence of dispensings of ≥ 5 oral medications over the respective 6-month periods [during the study window period (day 91 to day 270) compared to the 6-month period prior to mailing]. AD medications and the three potentially inappropriate medication classes will contribute to measure of polypharmacy. Injectables and topical or ocular medications will not be counted as evidence of polypharmacy.

A combination drug will be considered a single medication for the purpose of this analysis. Additional analyses will examine within-patient change in number of inappropriate medications, where the maximum possible decrease equals the pre-intervention number of inappropriate medications. We will accommodate this between-patient heterogeneity as follows: within-patient changes will be ranked separately by pre-intervention number of inappropriate medications, ranks will be transformed using normal scores to obtain comparable distributions across these strata, and treatment arms will be compared regarding transformed ranks³⁴ using analysis of covariance. In analyses of other secondary outcomes, count outcomes such as per-patient number of emergency department (ED) visits will be analyzed using Poisson or negative binomial regression, accounting for “excess” zeros if warranted based on observed distributions.³⁵

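### Section 9.4.3 gives no robust variance for days hospitalized or non-acute institutional days, and the count models that appear to cover them do not reliably give valid error bars for totals that accrue in whole stays

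*Combined protocol and SAP*

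**What the plan says.** Section 9.4.3, item c), lists among the secondary outcomes "overall health care utilization (number of outpatient visits, days hospitalized, emergency department visits, and non-acute institutional days". Two of these components, days hospitalized and non-acute institutional days, are sums of days. The others count events.

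The only model sentence that can cover them comes later in 9.4.3. Count outcomes, with per-patient ED visits as the example, "will be analyzed using Poisson or negative binomial regression", and the sentence goes on to allow for extra zeros where the observed distributions warrant it, citing a paper on zero-inflated and hurdle models. Day totals are not named there, so their coverage is an inference. If they are not covered, they have no stated analysis at all.

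No sandwich variance, quasi-likelihood scale, bootstrap or permutation method appears anywhere, and there is no rule for choosing among the models. Section 9.2 gives planning rates for events only ("mean of 0.35 hospitalizations per 6-month period and 0.4 ED visits per 6-month period") and no power statement for day totals.

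**The concern.** Poisson regression takes the variance to equal the mean, as if each day were a separate independent event. Negative binomial regression assumes a gamma-mixed Poisson count of days. Neither describes a total in which most patients have zero and the rest have one or more whole stays, up to the 180 days of the window. When the assumed variance is wrong, so are the model-based standard error, confidence interval and p-value.

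Section 9.1 counts overall utilization among the measures of reduced medication-related morbidity. Section 8.3 says adverse events are not ascertained, and 9.4.4 lists safety analyses as not applicable, so utilization is one of the few places where harm could show. Standard errors that are too small would turn chance differences in days into apparent effects of the mailing. Standard errors that are too large could hide a real fall or a real rise.

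**Working it through.** **Inputs from section 9.2.** Error rate: "overall Type I error rate of .05 with a Bonferroni correction for 3 pairwise comparisons of study arms (.05/3=.0167), and 2-sided hypothesis testing", giving a critical value z = 2.394. "The calculations below employ 80% power", giving z = 0.842. "Our target sample size for the first trial is 14,442 patients, 4814 patients in each of the three study arms". After the 9.9% loss before day 91, 4814 × 0.901 = 4337 per arm. Rates are 0.35 hospitalizations and 0.4 ED visits per patient per 6 months.

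**Assumed, because the documents are silent.** Stay lengths (hospital mean 3 to 8 days; institutional mean 10 to 40 days), their coefficient of variation (CV, 0 to 3), institutional stays per patient (0.05 to 0.15), and between-patient variation in the number of stays.

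**Step 1: the plan's own figure.** With plain Poisson variance,

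n per arm = (2.394 + 0.842)² × [1/μ + 1/(μ·RR)] / (ln RR)², where (2.394 + 0.842)² = 10.469 before rounding.

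- Hospitalizations, μ = 0.35, RR = 0.8856: 10.469 × (2.857 + 3.226) / 0.01476 = 4315.
- ED visits, μ = 0.40, RR = 0.8927: 10.469 × (2.500 + 2.800) / 0.01288 = 4307.

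Both are within 0.7% of 4337, so the stated ratios reproduce. They carry no overdispersion, and they concern events, not days.

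**Step 2: why Poisson fails for days.** If stays are Poisson and stay length has mean m and coefficient of variation c, then variance / mean of the day total = m(1 + c²). The Poisson standard error is therefore 1/√[m(1 + c²)] of the true one.

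- Hospital days, m = 5, c = 1: variance / mean = 10 and SE ratio 0.316. Null rejection = 2 × [1 − Φ(2.394 × 0.316)] = 45%.
- Institutional days, m = 25, c = 0.8: variance / mean = 41 and SE ratio 0.156. Null rejection = 2 × [1 − Φ(2.394 × 0.156)] = 71%.

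Between-patient variation in the number of stays makes this worse.

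**Step 3: simulation under the null.** Two arms of 4,337, stays drawn as Poisson or negative binomial, each stay given a length, totals capped at 180 days, 14 assumed scenarios (five for the hurdle negative binomial).

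| Analysis | Model SE / true SD | Null rejection |
|---|---|---|
| Poisson | 0.11–0.45 | 29%–78% at nominal 1.67% |
| Plain negative binomial, 11 of 14 scenarios | 1.19–1.73 | 0.1%–2.2% at nominal 5% |
| Plain negative binomial, hospital stays, CV 1.5 | 1.02 | 4.9% at nominal 5% |
| Plain negative binomial, hospital stays, CV 2 and CV 3 | 0.89 and 0.79 | 7.8% and 11.5% at nominal 5% |
| Hurdle negative binomial, overall mean ratio | 0.92–1.04 | 4.8%–7.0% at nominal 5% |
| Hurdle negative binomial, count-part coefficient | 0.87–1.12 | 2.0%–8.8% at nominal 5% |
| Log link with sandwich variance | 0.96–1.03 | 1.3%–2.5% at nominal 1.67% |

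A hurdle Poisson was run in seven scenarios (0.35 stays of mean 3 to 8 days; 0.05 to 0.15 stays of mean 10 to 40 days). At nominal 1.67% its count-part coefficient rejected 24% to 63% of the time and its overall mean ratio 4.9% to 8.4%, against 1.3% to 2.1% for robust variance.

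**Step 4: power at .0167.** For institutional days at 0.10 stays per patient, mean 25 days, CV 0.8, with 25% fewer stays in one arm, simulated power is 13% with plain negative binomial and 72% with robust variance. Closed form for the robust figure:

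- Mean days are 0.10 × 25 = 2.5 and 1.875.
- SE = √[(41/2.5 + 41/1.875)/4337] = 0.094.
- |ln 0.75| / 0.094 = 3.06, and Φ(3.06 − 2.394) = 75%, ignoring the cap and between-patient variation.

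For hospital days (mean stay 5 days, CV 1) at ratio 0.8856, power is 23% and 40%.

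**The case against.** The strongest reply is the clause on extra zeros. Simulated zeros ran from 74% to 96%, so an analyst would probably invoke it. A hurdle negative binomial then removes most of the problem for the overall mean ratio. In seven further scenarios its power was within 2 points of robust variance in six, and 11 points lower (41.8% against 52.8%) in the seventh, where institutional stay lengths had CV 1.5. That stands, and it rules out saying that the plan as a whole gives wrong error bars.

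It does not settle the matter. The option depends on the observed data. The plan does not say whether the overall mean ratio or the count-part coefficient would be reported. The same clause also allows Poisson-based versions, and the hurdle Poisson was anti-conservative on both contrasts.

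Two further replies are fair. Few analysts would keep Poisson when the variance is many times the mean and negative binomial is named beside it, so the Poisson figures show what the text permits, not what is likely. And for hospital days plain negative binomial is often serviceable: at a ratio of 0.80 with mean stays of 3, 5 and 8 days its power was 91%, 83% and 74%, against 98%, 96% and 92% with robust variance.

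A reader might also infer that the plan states a null of equal mean utilization. It does not: section 9.1 gives a null only for the primary endpoint and a directional hypothesis for the secondary ones.

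**Conclusion.** The concern holds in limited form. If day totals fall under the count-outcome sentence, the permitted analyses run from nearly calibrated (hurdle negative binomial, overall mean ratio) to badly anti-conservative (Poisson, about 30% to 78% null rejection at nominal 1.67%). Plain negative binomial is usually miscalibrated, mostly too wide, with substantial power loss for institutional days.

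A reader might go further and conclude that the error bars are wrong under either named model, or that negative binomial always hides real effects. The documents do not support that. The size and direction of the negative binomial error depend on the spread of stay lengths, which they do not give, and it was about right or too narrow for very skewed hospital stays.

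The sizes rest on assumed stay lengths, institutional-stay rates and between-patient variation. The simulations omit covariates and unequal follow-up, and zero-inflated models were not run. Only two components of one secondary outcome item are affected; the primary endpoint is not.

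**What to change.** In section 9.4.3, name days hospitalized and non-acute institutional days and state that arms will be compared as a ratio of mean rates from a log-link model with a log(observed days) offset and sandwich or patient-level bootstrap standard errors. Confidence intervals and p-values at .0167 should come from that variance. This also fixes the contrast, which the plan leaves open. Any hurdle or zero-inflated fit can be kept as a supporting analysis.

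The cost is one sentence of text and one option in the regression code, with no new data or patients. The drawbacks are slightly less exact intervals if stays prove very rare, and a small loss of power compared with a correctly specified model.

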9.4.4 SAFETY ANALYSES

N/A

9.4.5 BASELINE DESCRIPTIVE STATISTICS

Demographics and baseline characteristics. Baseline and demographic characteristics will be based on claims data at the time of randomization. Frequency distribution and summary statistics will be presented by three intervention groups. Key demographics to be summarized include age in 5-year categories, sex, ethnicity, geographic region, Combined Comorbidity score, health care utilization indices and current use of inappropriate prescribing drugs. Categorical variables will be presented as frequencies and continuous variables as mean and SD. We will not use inferential statistics at baseline.

9.4.6 PLANNED INTERIM ANALYSES

N/A

9.4.7 SUB-GROUP ANALYSES

We will conduct analyses stratified by sex and we do not anticipate sex related differences in within- group correlations (ICC). We will also conduct analyses of primary and secondary outcomes stratified by each individual drug class. Pre-specified analyses of primary and secondary outcomes will be conducted according to levels of polypharmacy at baseline (5+ medications at baseline; 7+ medications at baseline).

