9.4 STATISTICAL ANALYSES

9.4.1 GENERAL APPROACH

In descriptive analyses, treatment arms will be compared regarding key patient characteristics, including age, gender, and renewal of inappropriate prescriptions in days 1-90, using percentages for categorical characteristics and means (standard deviations) or medians (interquartile range) for continuous characteristics, depending on the observed distributions. Analyses of study outcomes will employ two-sided hypothesis testing and an overall Type I error of 0.05, applying a Bonferroni correction to accommodate three pairwise comparisons of the three study arms. Covariates of *a priori* interest include patient age, gender, and renewal of inappropriate prescriptions in the blackout period. In addition, we will adjust for characteristics that are found to predict study outcomes, in order to increase precision for the comparison of study arms,²⁸ as well as for characteristics found to be related to censoring or other missing data, in order to reduce possible nonresponse bias.²⁹ All analyses will be intention-to-treat. Sex as a biological variable will be factored into all analyses.

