9.4.9 EXPLORATORY ANALYSES

Analyses parallel to those conducted for the primary outcome will be conducted by targeted inappropriate medication class.

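### Section 9.4.7 uses overlapping polypharmacy levels (5+ and 7+) with no stated comparator, and no arm-by-subgroup interaction is pre-specified for polypharmacy, sex or drug class

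*Combined protocol and SAP*

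**What the plan says.** Section 9.4.7 (Sub-Group Analyses) makes three commitments.

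- Sex: "We will conduct analyses stratified by sex".
- Drug class: "We will also conduct analyses of primary and secondary outcomes stratified by each individual drug class".
- Baseline polypharmacy, for primary and secondary outcomes, at two levels: "5+ medications at baseline; 7+ medications at baseline".

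Section 9.4.9 (Exploratory Analyses) returns to class: "Analyses parallel to those conducted for the primary outcome will be conducted by targeted inappropriate medication class".

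Section 9.4.1 controls multiplicity by "applying a Bonferroni correction to accommodate three pairwise comparisons of the three study arms" and does not mention subgroups. It also says that sex will enter all analyses, which does not specify an interaction with arm. No section names an arm-by-subgroup term or a test of heterogeneity.

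Sections 1.1 and 4.1 say that the second trial will be adapted in light of the first, and list narrowing the targeted drug classes as one possible adaptation.

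**The concern.** A subgroup analysis is meant to show whether the effect differs between kinds of patient. The planned outputs do not address that question directly, for two separate reasons.

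**Polypharmacy.** The 7+ patients sit inside the 5+ group, so the two estimates share data. Their similarity is partly built in, and a real difference between patients on five or six drugs and those on seven or more is diluted. No group below five drugs and no five-to-six group is named.

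**Sex and class.** These strata do not overlap: the prioritisation in Section 4.1 assigns each patient to one class. But the plan stops at separate results. Without a pre-specified comparison, a reader may take significance in one stratum and not in another as evidence of a difference. Strata of unequal size often produce that pattern when the effect is identical.

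Class results are an obvious input if the classes for trial 2 are reconsidered, so a spurious class difference could carry weight beyond this trial.

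**Working it through.** **Inputs**

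- Section 9.2: 4,337 patients per arm reaching day 91; 13.5% censored in days 91-270; "Bonferroni correction for 3 pairwise comparisons of study arms (.05/3=.0167"), with "2-sided hypothesis testing"; worked example with 75% failures in Arm 1 and detectable HR 0.9165.
- Section 1.1: 68.2% women in the feasibility cohort, hence 31.8% men.
- Section 4.1, Table 1B, out of 26,259: antipsychotics 12,581 (47.9%), sedative-hypnotics 5,122 (19.5%), strong anticholinergics 8,556 (32.6%).

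**Step 1. Reproduce the plan's figure.** Uncensored patients per arm: 4,337 x (1 - 0.135) = 3,752. Arm 2 failure probability: 1 - (1 - 0.75)^0.9165 = 0.7193, as printed. Events: 3,752 x (0.75 + 0.7193) = 5,513. The Schoenfeld formula requires 4 x (2.394 + 0.842)^2 / (ln 0.9165)^2, about 5,509 events, for 80% power at two-sided 0.0167. The plan's inputs therefore give 80.0% power, as stated.

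**Step 2. Power within each stratum.** Split the 5,509 events by stratum share f and give every stratum the same true HR. Power = Phi( |ln 0.9165| x sqrt(5,509 f) / 2 - 2.394 ).

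| Stratum | Share | Events | Power |
|---|---|---|---|
| Women | 68.2% | 3,757 | 61% |
| Men | 31.8% | 1,752 | 28% |
| Antipsychotics | 47.9% | 2,639 | 44% |
| Sedative-hypnotics | 19.5% | 1,075 | 17% |
| Strong anticholinergics | 32.6% | 1,795 | 29% |

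**Step 3. Chance that strata disagree on significance when the effect is identical.**

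- Sex: 0.610 x 0.715 + 0.285 x 0.390 = 0.547, about 55%.
- Class: 1 - P(all significant) - P(none significant) = 1 - (0.439 x 0.167 x 0.292) - (0.561 x 0.833 x 0.708) = 1 - 0.021 - 0.331 = 0.648, about 65%.

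The plan does not say what threshold a subgroup reading would use. With 1.960 in place of 2.394 (two-sided 0.05), the same formulas give 53% for sex and 77% for class. If the trial's share of women were anywhere from 60% to 75% (assumed range), the sex figure at 0.0167 would run from 51% to 59%.

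**Step 4. The nested pair.** With a common effect and events proportional to patients, the correlation between the 5+ and 7+ estimates is sqrt(share in 7+ / share in 5+). The documents give neither share, so a range is assumed. Discordance on significance is by simulation.

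| Assumed share 5+ / 7+ | Correlation | Discordant |
|---|---|---|
| 90% / 70% | 0.88 | 17% |
| 80% / 60% | 0.87 | 20% |
| 80% / 50% | 0.79 | 28% |
| 70% / 40% | 0.76 | 31% |
| 60% / 30% | 0.71 | 33% |

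Illustration of masking at 80% / 50%, so 30% of patients take five or six drugs. With true HR 0.85 in 7+ and 1.00 in 5-6, the 5+ log HR is (50 x ln 0.85 + 30 x 0) / 80 = -0.102, an HR of about 0.90. The plan would report 0.85 beside 0.90, and the group with no effect would not be shown.

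**Step 5. What an interaction estimate could detect.** For one pair of arms, 80% power and two-sided 0.05, the detectable ratio of HRs is exp( -(1.960 + 0.842) x 2 x sqrt(1/d1 + 1/d2) ), with d1 and d2 the events in the two strata.

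- Women versus men: 0.85.
- Antipsychotics versus strong anticholinergics: 0.84.
- Antipsychotics versus sedative-hypnotics: 0.82.
- Fewer than five drugs versus five or more: 0.78, 0.83, 0.85 or 0.86 if 10%, 20%, 30% or 40% take fewer than five (assumed; not in the documents).

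**The case against.** Four stronger readings are tempting, and the documents do not support them.

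- **Patients on fewer than five drugs are left out.** The two levels may be cut-points, each with an implied complement (5+ versus <5, 7+ versus <7). Section 9.4.7 does not say so, but it does not exclude anyone either. What stands is that the comparator is unstated.
- **The analyses cannot show whether effects differ.** For sex and class the strata are disjoint, and their HRs with intervals can be compared afterwards. The gap is that no such comparison is pre-specified.
- **Subgroups will often look different by chance.** That fits sex and class, and only if results are judged by within-stratum significance, a rule that the plan does not adopt. For the nested pair the main effect is the reverse: shared patients make the two results look alike.
- **Class results are meant to decide trial 2.** Sections 1.1 and 4.1 present limiting the classes as a possibility, based on findings and experience generally, and Section 9.4.9 places the by-class primary analysis under exploratory work.

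There is also a fair objection to the remedy. The detectable ratios in Step 5 are all further from 1 than the overall detectable HR of 0.9165, so interaction tests will usually be inconclusive. Nor does an interaction show whether a given class benefits. Both points stand. They argue for descriptive labelling and for reading class-specific HRs alongside the interaction, not for leaving the comparison unspecified.

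**Conclusion.** The point holds as a low-cost improvement. Section 9.4.7 names overlapping polypharmacy levels without a comparator and offers only stratified results for sex and class, and no interaction is pre-specified anywhere.

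The masking example (0.85 beside about 0.90) and the correlations of 0.71 to 0.88 rest on assumed shares and effects. The discordance figures of 55% and 65% rest on a common HR of 0.9165, feasibility-cohort shares, the same 75% failure rate in every stratum, and a significance-by-stratum reading that the plan does not prescribe. The trial keeps one randomly chosen patient per prescriber (Sections 4.1 and 6.3), so its mix may differ from the feasibility cohort. The primary comparison of arms is untouched.

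**What to change.** In Section 9.4.7:

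1. Replace the two polypharmacy levels with disjoint ones (<5, 5-6, >=7 oral drugs at baseline), or use the baseline drug count as a continuous effect modifier.
2. Add arm-by-subgroup terms for sex, drug class and polypharmacy, and report the interaction estimates with confidence intervals, labelled descriptive.
3. State that any claim of differing effects rests on those estimates, not on which strata reach significance.
4. If class results inform the trial 2 adaptation, consider the class-specific HRs with their intervals together with the interaction estimate; neither alone is enough.
5. State the low power: detectable ratio of HRs about 0.85 for sex and 0.82 to 0.84 for antipsychotics versus each other class, at 80% power and two-sided 0.05.

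The cost is a few sentences and a few model terms, with no new data. The drawback is that most interaction intervals will be wide.
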